7.7 Follow-up of subjects withdrawn from treatment

Withdrawn subjects are encouraged to complete final assessments for intention-to-treat analysis where possible.

7.8 Premature termination of the study

The study may be terminated early if significant safety concerns arise, futility is evident, or upon recommendation of the Ethics Committee.

8. SAFETY REPORTING

8.1 AEs, SAEs and SUSARs

8.1.1 Adverse events (AEs)

An adverse event (AE) is defined as any untoward medical occurrence, unintended symptom, or clinical worsening in a study participant during the study period (from informed consent to final assessment), whether or not considered related to the study interventions (structured exercise, intergenerational activities, nutritional education, assessments, or blood sampling).

All AEs are recorded by the research team:

- Spontaneously reported by participants (elderly or children via orphanage representative).
- Observed during sessions, monitoring calls, or assessments (e.g., fatigue, muscle soreness, minor bruising from blood draw, emotional discomfort).
- Elicited during routine queries (e.g., weekly pre-exercise checks, bi-weekly evaluations, post-session feedback).

AEs are documented in the case report form (CRF) with details on description, onset date, severity (mild/moderate/severe), duration, relationship to intervention (unlikely/possible/probable), actions taken, and outcome. Mild AEs (e.g., transient muscle soreness, initial awkwardness in interactions) are managed supportively (rest, reassurance, session adjustment).

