5.2 Use of co-intervention (if applicable)

Co-interventions are minimized and monitored:

- Routine medications and medical care are permitted and recorded.
- Additional structured exercise or intergenerational programs outside the study are not allowed during the 16-week period and will be queried at follow-up visits.
- Both arms receive identical monitoring (phone counseling 2–3 times/month) to encourage adherence and prevent dropout.

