7.1.3. Other parameters (exploratory)

- Adherence to exercise sessions and intergenerational activities (attendance logs).
- Nutritional status (Mini Nutritional Assessment, MNA).
- Physical activity level (Physical Activity Scale for the Elderly, PASE).
- Depressive symptoms (Geriatric Depression Scale-15, GDS-15).
- Loneliness (De Jong Gierveld Loneliness Scale, Indonesian version).
- Quality of life additional domains (EQ-5D-5L).
- Charlson Comorbidity Index (CCI).
- Adverse events and dropout reasons.

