7.3.8 Monitoring and adherence

Adherence and safety are monitored proactively to maximize retention and minimize risks.

- Adherence monitoring:
 - Exercise sessions (intervention arm): Attendance logged by instructor and research assistant; session completion confirmed ($\geq 85\%$ of planned sessions required for per-protocol analysis).
 - Intergenerational activities: Attendance sheets signed by research team and orphanage staff; activity completion checklists.
 - Nutritional education (both arms): Confirmation of tele-conference attendance and e-flyer receipt/viewing (via read receipts or follow-up query).
 - Overall: Monthly telephone counseling (2–3 calls/month) by research team to encourage compliance, address barriers, and reinforce motivation.
- Safety monitoring:
 - During exercise phase: Weekly (Monday) pre-session symptom and condition checks by team/instructor; Borg Rating of Perceived Exertion scale monitored throughout sessions; immediate termination for excessive symptoms (severe dyspnea, palpitations, dizziness, heavy weakness, pre-syncope).
 - Bi-weekly direct evaluations (weeks 4, 6, 8, 10): Remote or in-person query on complaints, with direct supervision during selected sessions.
 - Intergenerational phase: On-site supervision by research team and orphanage staff; post-session brief feedback on comfort/discomfort.
 - General: Participants provided with contact number for immediate reporting; all potential adverse events (fatigue, muscle pain, emotional discomfort, minor injuries) documented, managed, and reported to Ethics Committee if serious.

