7.4 Study visits

Study visits are scheduled to minimize burden while ensuring complete data collection. Visits occur at community centers, participant homes (if needed), or orphanages.

- Screening/Baseline visit (week 0, 1–2 days):
 - Explanation of study, informed consent (elderly and orphanage for children).
 - Medical history, comorbidity assessment (CCI), medication review.
 - Full physical examination, vital signs, anthropometry.
 - Cognitive (MoCA-Ina), physical (hand-grip strength, gait speed), functional (IADL), frailty (CHS), nutritional (MNA), and psychological assessments.
 - All questionnaires (SF-12, EQ-5D-5L, GDS-15, PASE, loneliness scale).
 - Blood sampling.
 - Randomization (post-eligibility confirmation).
 - Nutritional education initiation (first tele-conference scheduling).

- Intermediate visit (end of week 12, post-exercise phase):
 - Repeat anthropometry, vital signs.
 - Physical performance (hand-grip strength, gait speed), frailty status.
 - Cognitive (MoCA-Ina) and selected questionnaires (SF-12, EQ-5D-5L, GDS-15, loneliness).
 - Blood sampling.
 - Adherence review; ToT preparation for SHP (intervention arm).
- Final visit (end of week 16):
 - Comprehensive repeat of baseline assessments (all physical, cognitive, functional, nutritional, psychological, and questionnaires).
 - Blood sampling.
 - Adherence summary, adverse event review.
 - Compensation distribution (transport reimbursement, snacks provision during study).
- Ongoing visits/activities:
 - Exercise: Weekly tele-sessions (intervention group).
 - Intergenerational: 8 in-person sessions at orphanages (weeks 13–16).
 - Nutritional: 2 tele-conferences + 5 e-flyers (both groups).
 - Monitoring calls.

Home visits arranged if mobility limits attendance.

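### Scheduled questioning about adverse events is more frequent in the intervention arm on every reading, and none is listed at week 12, so adverse-event tables by arm will not be comparable

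*Combined protocol and SAP*

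**What the plan says.** Section 8.1.1 defines an AE for every participant, related to the interventions or not, and gives three routes of recording: spontaneous report, observation (at sessions, calls or assessments), and active questioning. The examples of the last route are "Elicited during routine queries (e.g., weekly pre-exercise checks, bi-weekly evaluations, post-session feedback".

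Section 7.3.8 shows where those examples sit. Under the exercise phase it lists "Weekly (Monday) pre-session symptom and condition checks by team/instructor". Under the intergenerational (SHP) phase it lists "post-session brief feedback on comfort/discomfort". A separate safety bullet, with no arm named, reads "Bi-weekly direct evaluations (weeks 4, 6, 8, 10): Remote or in-person query on complaints, with direct supervision during selected sessions". Section 7.3.7 also lists a symptom query before exercise sessions, under the intervention group.

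For contact common to both arms, section 5.2 says: "Both arms receive identical monitoring (phone counseling 2–3 times/month) to encourage adherence and prevent dropout". Section 7.3.8 describes these calls only in terms of compliance, barriers and motivation, and gives participants a number to ring. In section 7.4 the week-12 visit ends with "Adherence review; ToT preparation for SHP (intervention arm", with no AE item. The week-16 visit has "Adherence summary, adverse event review".

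Section 7.1.3 lists "Adverse events and dropout reasons" as an exploratory parameter. Section 9 contains no AE analysis.

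**The concern.** The expected events in section 6.4 (fatigue, soreness, dizziness after venipuncture, initial awkwardness) are mainly mild and short-lived. How many such events are counted depends heavily on how often people are asked. If one arm is asked at its sessions and the other mainly at the end, a table of AEs by arm mixes true harm with unequal questioning.

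At stake is the control arm's role as a background rate. A recorded excess under intervention could be real or could come from the extra questions, and the data would not separate the two. The ambiguity cuts both ways: a spurious excess may be read as harm, and a true one may be explained away. Section 8.5 sets up no independent safety board and relies on the investigator noticing patterns of AEs, so the tables should be interpretable. Section 7.2 describes an unblinded research team, which adds to the concern; section 5 says that investigators and participants are blinded, and the two passages must be reconciled.

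**Working it through.** **The plan's own figure.** The documents give no AE rate, AE power or count of AE queries. The only design figure used below is 50 per arm. Section 4.5 gives a largest requirement of 42 per group and section 7.6 a drop-out rate of up to 15%: 42 / (1 − 0.15) = 49.4, rounded up to 50, which agrees with the plan.

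**Inputs for the count of scheduled queries per participant**
- Weekly pre-session checks over 12 exercise weeks: 12 (7.3.8).
- If every exercise session has a symptom query (7.3.7): 2×1 + 4×2 + 6×3 = 28 sessions (5.1), replacing the 12.
- Bi-weekly evaluations at weeks 4, 6, 8 and 10: 4 (7.3.8).
- Feedback after SHP sessions: 8 (5.1, 7.3.8).
- AE review at week 16: 1, both arms (7.4).
- Calls: 2–3 a month over four 4-week months = 8 to 12, both arms (5.2).

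**Results**

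| Reading | Intervention | Control | Ratio |
|---|---|---|---|
| Calls not counted; bi-weekly in intervention arm only | 12+4+8+1 = 25 | 1 | 25 |
| Same, query at every exercise session | 28+4+8+1 = 41 | 1 | 41 |
| Calls not counted; bi-weekly in both arms | 25 | 4+1 = 5 | 5 |
| Calls counted; bi-weekly in intervention arm only | 33 to 37 | 9 to 13 | 3.7 to 2.8 |
| Calls counted; bi-weekly in both arms | 33 to 37 | 13 to 17 | 2.5 to 2.2 |

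The last row is the reading most favourable to the plan, and the imbalance is still at least about 2.2-fold.

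**What unequal questioning could do (all rates assumed).** Let the true risk p be the same in both arms, with capture probability 0.9 under intervention and c under control. The reported risks are 0.9p and cp, so the spurious risk ratio is 0.9/c whatever p is:
- c = 0.7: 0.9/0.7 = 1.29
- c = 0.5: 0.9/0.5 = 1.8
- c = 0.3: 0.9/0.3 = 3.0

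With p = 30%, the reported risks are 27% against 21%, 15% or 9%. If someone ran a two-sided 5% two-proportion test with 50 per arm, the approximate chance of a nominally significant excess is Φ[(difference − 1.96·SE0)/SE1], where SE0 is the pooled and SE1 the unpooled standard error. For 27% against 15%, SE0 = √(2×0.21×0.79/50) = 0.0815 and SE1 = √((0.27×0.73 + 0.15×0.85)/50) = 0.0806. That gives Φ[(0.12 − 0.160)/0.0806] = 0.31. The other two cases give about 0.10 (c = 0.7) and 0.65 (c = 0.3). Over p from 20% to 40%, the range is about 0.08 to 0.81.

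**The case against.** The strongest reply has four parts.

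First, the plan makes no between-arm AE comparison. Section 9 lists the outcomes to be compared and AEs are not among them. This stands: no primary or secondary endpoint is affected, and the significance calculation above describes a test the plan does not contain.

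Second, the control arm has real routes of capture. Section 8.1.1 names calls and assessments as AE sources, its list of elicited sources is only by example, and participants have a contact number. This stands in part. A reader might infer that AEs are sought only in the intervention arm, or that controls are first asked at week 16. The documents do not support either as fact, because AEs may be noted at calls and at the week-12 assessments. But the calls are described as adherence support with no AE question specified, and counting every call as a query still leaves the imbalance.

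Third, the bi-weekly evaluations name no arm. True; placing them in the intervention arm is the more natural reading because they mention supervised sessions, but it is an inference. Giving them to both arms does not equalise the schedule.

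Fourth, closer checks on people who exercise are good safety practice, and the bias runs against the intervention. Both are fair. The checks should stay. The problem is only that their yield would be tabulated beside an arm without them.

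A reader might also infer that control-arm hospitalisations would be missed. The text does not show this: serious AEs have their own reporting rule (8.1.2) and acute illness is a withdrawal ground in both arms (7.5, 7.5.1). Nor does the point overturn the minimal-risk conclusion in section 12.2, which is a prospective assessment and not a trial result.

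**Conclusion.** The point holds, limited to descriptive safety reporting. Scheduled questioning about AEs is unequal on every reading, from about 25 against 1 to about 37 against 17, and no AE review is listed at week 12. AE tables by arm built from all sources would not be comparable, and the likely direction is more AEs recorded under intervention.

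The size cannot be derived from the documents. The spurious risk ratio of about 1.3 to 3.0 rests on assumed capture of 90% under intervention and 70% to 30% under control, with equal true risk.

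A reader might infer that a statistically significant false excess is to be expected. That depends wholly on the assumption. With a true risk of 40% and 50 per arm, control capture of 40% gives 18 against 8 (z = 0.20/0.0877 = 2.28, p about 0.02). Control capture of 70% gives 18 against 14 (z = 0.08/0.0933 = 0.86, p about 0.39).

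**What to change.** In sections 8.1.1, 7.3.8 and 7.4:
- Put the same short scripted AE checklist, including falls, acute illness and hospitalisation, on the existing 2–3 calls a month in both arms.
- Add an AE review to the week-12 visit.
- State which arm or arms the bi-weekly evaluations cover.
- Base any between-arm AE table on these common sources. Report events found through exercise checks and SHP feedback separately, as descriptive intervention-arm data.
- Keep all session-based safety checks unchanged.

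The common schedule would then be 8–12 calls plus weeks 12 and 16, that is 10–14 queries in each arm. The cost is one case report form page and a few minutes on contacts that already take place, with no new visits or staff. The downside is slightly longer calls and more control-arm AEs to document.

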8.1.2 Serious adverse events (SAEs)

A serious adverse event (SAE) is any AE that:

- Results in death.

- Is life-threatening (immediate risk of death).
- Requires hospitalization or prolongation of existing hospitalization.
- Results in persistent or significant disability/incapacity.
- Constitutes any other medically important event (e.g., acute illness requiring urgent intervention that significantly impacts study participation or health).

Given the low-risk nature of the interventions, SAEs are expected to be rare and mostly unrelated (e.g., acute unrelated illness in elderly). All SAEs are reported to the principal investigator immediately (within 24 hours of awareness) and to the approving Ethics Committee (Komite Etik Penelitian Kedokteran FKUI-RSCM or equivalent) within 15 days. SAEs resulting in death or life-threatening are reported expedited (initial report within 7 days, complete follow-up within additional 8 days).

8.2.3 Suspected unexpected serious adverse reactions (SUSARs)

Not applicable. As this is a non-medicinal product study with established low-risk behavioral interventions (PEROSI chair-exercise and intergenerational programs), no unexpected serious reactions attributable to an investigational product are anticipated.

8.3 Annual safety report

An annual safety report summarizing all AEs and SAEs (including relatedness assessment and cumulative overview) will be submitted to the Ethics Committee if the study duration exceeds one year or upon request. The report includes participant enrollment status, deviations, and any emerging safety concerns.

8.4 Follow-up of adverse events

All AEs and SAEs are followed until resolution, stabilization, or return to baseline. Follow-up may include:

- Additional phone contacts or visits.
- Medical referral (e.g., to geriatrician or primary care physician).
- Repeat assessments if clinically indicated.
- Documentation of outcome (recovered, ongoing, sequelae).

Participants withdrawn due to AEs/SAEs receive continued safety monitoring

8.5 Data Safety Monitoring Board (DSMB) / Safety Committee

Not applicable. Given the minimal risk profile of the interventions (community-based exercise and social activities in screened healthy/cooperative participants), no independent Data Safety Monitoring Board is established. Safety oversight is provided directly by the principal investigator and supervisor. Any emerging patterns of AEs will prompt ad-hoc review and consultation with the Ethics Committee if needed.

9. STATISTICAL ANALYSIS

All collected data will be initially recorded on research case report forms (CRFs) and subsequently transferred to secure electronic storage for data cleaning, coding, and verification. Descriptive data and analytical results will be presented in narrative text, tables, or figures as appropriate.

Normality of data distribution will be assessed using the Kolmogorov-Smirnov or Shapiro-Wilk test ($p > 0.05$ indicates normal distribution). Normally distributed continuous data will be presented as mean \pm standard deviation (SD); non-normally distributed data as median with minimum-maximum range. Categorical data will be presented as frequencies and percentages. Statistical significance will be set at $p < 0.05$. All analyses will be performed using SPSS version 20 software.

Primary analyses will be conducted on the per-protocol (PP) population, excluding drop-out subjects. Between-group comparisons of changes in study outcomes (hand grip strength, gait speed, MoCA-Ina score, serum mBDNF levels, and health-related quality of life) will use unpaired t-tests (parametric) or Mann-Whitney U tests (non-parametric), selected based on normality test results.

Correlations between serum mBDNF levels and MoCA-Ina score, hand grip strength, and gait speed will be evaluated using Pearson correlation (for normally distributed variables) or Spearman correlation (for non-normally distributed variables), according to normality assessment of each variable.

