3. STUDY DESIGN

This is a single-center, randomized, open-label (unblinded), parallel-group controlled clinical trial evaluating the efficacy of a sequential multimodal intervention (structured physical exercise followed by SHP-based intergenerational activities) compared to nutritional education alone in community-dwelling elderly aged 60–75 years with physio-cognitive decline syndrome (PCDS).

The study duration per participant is 16 weeks, consisting of:

- Baseline assessment (week 0)
- Intervention period: 12 weeks of chair-exercise + 4 weeks of intergenerational activities (intervention arm) or continued education (control arm)
- Intermediate assessment (end of week 12)
- Final assessment (end of week 16)

Participants are randomized in a 1:1 ratio into two arms:

- Intervention arm (n=50): Nutritional education + 12 weeks structured chair-based exercise (PEROSI protocol, progressive frequency from 1 to 3 sessions/week, 60 minutes/session, supervised online) followed sequentially by 4 weeks SHP-based intergenerational activities (8 sessions, 2x/week, 45 minutes/session, paired 1:1 elderly-child using AMIR educational materials at selected orphanages).
- Control arm (n=50): Nutritional education only (2 personalized dietitian tele-conferences at weeks 1 and 11; 5 educational e-flyers at weeks 3, 5, 7, 13, and 15).

Randomization is computer-generated using permuted block randomization (block size 4), stratified if necessary, with allocation concealment managed by an independent third party. Blinding of participants and instructors is not feasible due to the nature of the behavioral interventions; however, outcome assessors for laboratory analyses (mBDNF) are blinded to group allocation where possible.

The trial follows intention-to-treat principles with per-protocol sensitivity analysis. Recruitment targets consecutive eligible elderly from community programs under the School of Medicine and Health Sciences at Atma Jaya Catholic University of Indonesia and the Archdiocese of Jakarta. Child participants (aged 5–8 years, n=50) are recruited from cooperating orphanages exclusively for the intervention arm.

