7.5 Withdrawal of individual subjects

Participants (elderly or children via orphanage representative) may withdraw voluntarily at any time without providing reasons and without impact on routine care or relationship with researchers. Withdrawal is documented but no further study procedures performed unless consented for final assessment.

Investigator-initiated withdrawal occurs for:

- Development of exclusion criteria (e.g., new disability, dementia suspicion, uncontrolled chronic disease).
- Acute illness requiring hospitalization or prohibiting continuation (e.g., pneumonia, acute stroke, uncontrolled hypertension).
- Non-adherence (>3 consecutive missed exercise sessions or <85% overall intervention completion).
- Intolerable adverse events suspected related to intervention.

Withdrawn participants are encouraged to complete safety follow-up and/or final assessments for intention-to-treat analysis. All withdrawals are fully documented (reason, date, partial data

collected) and reported to Ethics Committee if related to safety. No replacement of withdrawn subjects.

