7.5.1 Drop out Criteria

Subjects are classified as drop-outs if they do not complete the study protocol through the final assessment (week 16) for any reason. Specific drop-out criteria include:

- Non-adherence to intervention: Failure to attend >3 consecutive structured exercise sessions (intervention arm) or $<85\%$ of total planned exercise sessions; failure to attend ≥ 2 intergenerational activity sessions or $<85\%$ overall attendance for SHP phase.
- Development of exclusion criteria during study: New onset of disability, suspected/confirmed dementia, depression (GDS-15 score indicating moderate-severe depression requiring intervention), total immobility, uncontrolled chronic disease, or hemodynamic instability.
- Acute illness or clinical worsening: Occurrence of acute conditions (e.g., pneumonia, acute arthritis with VAS $>6/10$, acute stroke, acute myocardial infarction, uncontrolled hypertension $\geq 180/100$ mmHg, acute COPD exacerbation) requiring hospitalization or prohibiting continuation.
- Adverse events suspected related to intervention: Intolerable or serious symptoms (e.g., persistent severe fatigue, muscle pain, dizziness, fall during exercise, significant emotional distress during intergenerational activities) leading to investigator decision for withdrawal.
- Voluntary withdrawal: Subject (or orphanage representative for children) requests discontinuation for any personal reason (e.g., lack of time, loss of motivation, transportation difficulties).
- Loss to follow-up: Inability to contact subject despite ≥ 3 attempts via phone/WhatsApp over 2 weeks, or permanent relocation outside study area.
- Death: Any mortality during study period (reported immediately as serious adverse event).

All drop-outs are documented in detail (date, reason, last completed assessment/procedure) on the case report form and in the trial master file.

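### Section 9 makes the per-protocol set primary, against section 3's intention-to-treat principle, and its attendance exclusions can remove only intervention participants

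*Combined protocol and SAP*

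**What the plan says.** Section 9 (Statistical Analysis): "Primary analyses will be conducted on the per-protocol (PP) population, excluding drop-out subjects". It names no ITT population, no ITT analysis and no method for missing data.

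Section 3 (Study Design): "The trial follows intention-to-treat principles with per-protocol sensitivity analysis".

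Section 7.5: "Withdrawn participants are encouraged to complete safety follow-up and/or final assessments for intention-to-treat analysis". Section 7.7: "Withdrawn subjects are encouraged to complete final assessments for intention-to-treat analysis where possible".

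Section 7.3.8 sets 85% "of planned sessions required for per-protocol analysis", under the exercise sessions of the intervention arm. For the education that both arms receive, it asks only for a record: "Nutritional education (both arms): Confirmation of tele-conference attendance and e-flyer receipt/viewing". No threshold is attached.

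Section 7.5.1 defines drop-outs more widely. The first criterion begins "Non-adherence to intervention: Failure to attend >3 consecutive structured exercise sessions (intervention arm" and goes on to cover attendance below 85% of exercise sessions, two or more missed SHP sessions, and SHP attendance below 85%. A further criterion, open to both arms, includes "New onset of disability, suspected/confirmed dementia, depression" (the last qualified as moderate to severe and needing intervention). Section 5.1 confirms that controls take no part in exercise or SHP sessions.

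Section 7.6 says the 50 per group already allow for up to 15% drop-out.

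**The concern.** There are two problems.

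First, the current text gives two incompatible primary analyses. Two analysts following it could report different primary results, and the choice could be made after the data are seen.

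Second, the set that section 9 makes primary is not protected by randomisation. A randomised intervention participant can be removed for attendance, but no control can be removed under the same rules. If attendance is related to 16-week change in grip strength, gait speed, MoCA-Ina or mBDNF, comparing selected attenders with unselected controls shifts the between-arm difference even when the intervention does nothing.

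Some drop-out criteria that apply to both arms, chiefly new disability and suspected dementia, also lie close to the outcomes. The direction of that bias is not fixed. If the intervention works, more worsening controls may be removed and the estimate pulled towards no effect.

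**Working it through.** **The plan's own figure.** Section 4.5 gives a largest requirement of 42 per group (two-sided 5%, 80% power). With the 15% in section 7.6, 42 / 0.85 = 49.4, rounded up to 50. This reproduces. The documents give no difference or SD. Inverting the two-means formula, the standardised difference implied by 42 is d = (1.960 + 0.842) × √(2/42) = 0.611.

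**Attendance thresholds.** Exercise sessions (section 5.1): 2×1 + 4×2 + 6×3 = 28, and 0.85 × 28 = 23.8, so at least 24 are needed. SHP sessions: 0.85 × 8 = 6.8, so at least 7 of 8. Controls have no sessions to which these rules apply.

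**Share of the intervention arm excluded by attendance.** The documents give no expected attendance, so mean attendance is an assumption. With independent sessions, the share is 1 − P(X ≥ 24 of 28) × P(Y ≥ 7 of 8). The clustered column draws each person's attendance probability from a beta distribution with ICC 0.05 to 0.5 (assumption).

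| Mean attendance | 7.5.1 rules, independent | 7.5.1 rules, clustered | 7.3.8 exercise rule only, independent |
|---|---|---|---|
| 95% | 7% | 10-14% | 1% |
| 93% | 14% | 15-21% | 4% |
| 90% | 30% | 20-32% | 14% |

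Adding the rule on more than three consecutive misses changes these shares negligibly. At 90% attendance, about 34 to 40 of 50 remain (50 × 0.68 to 50 × 0.80) before any other loss, against the 42 required.

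**Bias with no true effect.** Let q be the fraction removed from the low end of attendance and ρ the correlation between attendance and outcome change (assumption). The mean of those kept shifts by ρ·φ(z_q)/(1 − q) SD. For q = 0.15 and ρ = 0.5: 0.5 × 0.233 / 0.85 = 0.137. If controls are lost by the same mechanism, their own term is subtracted; if they are lost at random, nothing is subtracted. Type I error is for a two-sided t-test, from 40,000 simulated trials per cell with 50 randomised per arm.

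| Intervention v control excluded | Control loss | Shift in SD, ρ 0.2 / 0.5 | Type I error, ρ 0.2 / 0.5 |
|---|---|---|---|
| 15% v 5% | random | 0.055 / 0.137 | 5.7% / 10.0% |
| 15% v 5% | same mechanism | 0.033 / 0.083 | 5.2% / 6.7% |
| 15% v 10% | same mechanism | 0.016 / 0.040 | 5.1% / 5.5% |
| 30% v 5% | random | 0.099 / 0.248 | 7.2% / 20.2% |
| 30% v 5% | same mechanism | 0.078 / 0.194 | 6.4% / 14.3% |
| 30% v 10% | same mechanism | 0.060 / 0.151 | 5.9% / 10.9% |

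As a fraction of d = 0.611, this runs from 0.016/0.611 = 3% to 0.248/0.611 = 41%. At ρ = 0.1 the shift is at most 0.05 SD and the type I error at most 5.6%.

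**Power** (normal approximation, d = 0.611).

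- ITT, 50 v 50, complete data: 86%, 83%, 79% and 74% at 0, 5, 10 and 15% dilution of the effect.
- ITT with 15% of week-16 data missing (42.5 v 42.5): 81% with no dilution, 72% at 10%.
- Per-protocol with no dilution: 82% at 42.5 v 47.5 (15% and 5% excluded), 78% at 35 v 47.5 (30% and 5%).

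**The case against.** The strongest reply accepts the contradiction and disputes the rest.

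- *Controls may face a threshold too.* Section 7.5 withdraws people below 85% of overall intervention completion, and section 5.1 treats education as a base intervention for both arms. That reading is possible, but no control threshold is defined, section 7.5.1 names only exercise and SHP sessions, and two teleconferences plus five flyers would not be an equal filter.
- *The 15% is an overall allowance.* This is right. With 15% lost in both arms by the same mechanism, the shift is zero. The unequal splits above are assumptions, not the plan's expectation.
- *The sign and size of the correlation are assumed.* This also stands. Poor attenders could start lower and change more, which would reverse the shift. The plan's calls and transport may keep attendance high. The 20% error is the worst corner of the table.
- *42 belongs to the most demanding outcome.* True. At the other end of the range, 9 per group, d = 2.802 × √(2/9) = 1.32, and the largest shift is 0.248/1.32 = 19% of it. Frailty status, a primary endpoint, is not among the outcomes listed for sample size or for the section 9 comparisons, so none of these figures covers it.
- *Most listed acute illnesses are not outcome decline.* Fair. The closeness to outcome rests mainly on disability and dementia.
- *Using all available week-16 data does not remove selection if low attenders never return.* True, so obtaining those assessments matters as much as the wording.

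These points limit the illustration. None of them removes the contradiction or the one-arm attendance filter.

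**Conclusion.** The concern holds and should be corrected before outcome data are analysed. Two findings rest on the text alone: section 9 contradicts sections 3, 7.5 and 7.7 on the primary population, and the attendance exclusions in sections 7.3.8 and 7.5.1 can be met only by intervention participants. The size of the bias cannot be derived from the documents. It ranges from negligible to about a quarter of an SD, depending on assumed attendance, control loss and the attendance-change correlation. A further consequence is that the 15% allowance must absorb every low attender as well as ordinary losses. At 90% mean attendance (assumption), the attendance rules alone would take the intervention arm below 42.

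**What to change.** - **Section 9:** define the primary population as all randomised participants, analysed in their allocated arm, using every available week-16 assessment whatever the attendance. Keep per-protocol as the sensitivity analysis, as section 3 already says. A mixed model that also uses the week-12 data is optional.
- **Section 7.5.1:** for analysis purposes only, class low attendance as non-adherence rather than study drop-out, and seek the week-16 assessment from these people, as sections 7.5 and 7.7 already encourage. The rules for stopping the intervention, including those in section 7.5, are not affected.
- **Section 7.6:** apply the 15% to missing week-16 assessments.

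The cost is wording in three sections and the effort of obtaining assessments that are now only encouraged and that need consent after voluntary withdrawal. Keeping non-attenders may dilute the effect. For the outcome needing 42 per group, power stays at or above about 79% up to 10% dilution with complete data, but falls to 72% if 15% of week-16 data are also missing. Per-protocol does not avoid a loss of power either, because it discards participants.
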